
Corrections of minor errors and typos:
 
 The approximate number of participants in second interim analysis was changed from 400 to 355 Collection of the optional genomics blood sample was moved from Screening Visit 1 to Day 1, Visit 3, and a note was added to clarify that if for any reason the sample is not drawn at Visit 3, it may be taken at any visit until the last study visit. CCI [REDACTED] The cross-references for albumin-to-creatinine ratio were updated to Section 8.6.1 The note '(after the 9th dose)' was removed for the Day 253 Echocardiogram The requirement of syringes to have appropriate covers and/or shields was replaced with a statement clarifying that syringes containing MEDI6570 look identical to those containing placebo. Text was amended as follows: 'It may be necessary for a participant to discontinue (definitive discontinuation) study intervention temporarily or permanently.' 	
 Correction of typo for number of participants To correct an error in the Schedules of Activities and to reduce the sampling burden on participants who may fail screening Correction of typo To correct error and guide reader to the appropriate location Correction of typo Correction of error; there are no visual differences between the IMP and placebo. To remove unnecessary text 	
 Section 1.1 Synopsis; Section 4.1 Overall design; Section 9.5 Interim Analyses Section 1.3 Schedule of Activities, Table 3 and Table 4; Appendix D, Optional Genomics Initiative Sample Section 1.3, Schedule of Activities, Table 4 Section 1.3 Schedules of Activities, Table 4 and Table 5 Section 1.3 Schedules of Activities, Table 5 Section 6.2.3 Dose Preparation Steps (Subcutaneous Dose Preparation) Section 7.1 Discontinuation of Study Intervention

Description of Change	Brief Rationale	Sections Affected

 ‘neutrophils’ was replaced with ‘buffy coat’ Updated footer text table for abbreviation for HCV DNA to HBV DNA Added italic font to table The year of the Zhang et al reference was corrected from 2008 to 2009 in the hyperlink In-text definitions of abbreviations at first use were removed 	
 To correct the terminology Corrected typo in footer text Italic type was missing from the table. Updated to align with table footer. Correction of typo For consistency with style conventions 	
 Section 8.6 Human Biological Sample Biomarkers Appendix E 6 Laboratory Tests Appendix F Intensity Categories for Statin Therapy Section 11 Reference List Throughout

ADA(s), anti-drug antibody(ies); AE, adverse event; BP, blood pressure; C_{max}, maximum observed concentration; COVID-19, Coronavirus disease caused by the novel severe acute respiratory syndrome coronavirus 2 (SARS-CoV-2); CTA, computed tomography angiography; CV, cardiovascular; ECG, electrocardiogram; DMC, data monitoring committee; eGFR, estimated glomerular filtration rate; FDA, Food and Drug Administration; HBV DNA, hepatitis B virus deoxyribonucleic acid; HF, heart failure; **CCI** [REDACTED] IMP, investigational medicinal product; MACE, major adverse cardiovascular events; MI, myocardial infarction; **CCI** [REDACTED] No, number; NT-proBNP: N-terminal prohormone brain natriuretic peptide; NSAID, non-steroidal anti-inflammatory drug; PK, pharmacokinetic; PPI, proton pump inhibitor; **CCI** [REDACTED] t_{1/2}, half-life

LN	Normal Logarithm
LOCF	Last Observation Carried Forward
LVEF	Left Ventricular Ejection Fraction
LSmeans	Least-Square Means
MACE	Major Adverse Cardiovascular Event
MedDRA	Medical Dictionary for Regulatory Activities
MI	Myocardial Infarction
MMRM	Mixed Model Repeated Measures
CCI	
NC	Not Calculable
NCPV	Non Calcified Plaque Volume (Global)
NCPV _{MD}	Non Calcified Plaque Volume in The Most Diseased Coronary Segment
NT-proBNP	N Terminal Prohormone Brain Natriuretic Peptide
NQ	Not Quantifiable
NR	Not Reportable
NS	No Sample
NSTEMI	Non-ST Segment Elevation Myocardial Infarction
PDMP	Protocol Deviation Management Plan
PCI	Percutaneous Coronary Intervention
PK	Pharmacokinetics
PT	Preferred Term

Abbreviation or special term	Explanation
Q4W	Every 4 Weeks
REML	Restricted Maximum Likelihood
SAE	Serious Adverse Event
SAP	Statistical Analysis Plan
SC	Subcutaneous
SD	Standard Deviation
SE	Standard Error
SI	International System of Units
CCI	[REDACTED]
SOC	System Organ Class
SQRT	Square Root
STEMI	ST Segment Elevation Myocardial Infarction
TEAE	Treatment Emergent Adverse Event
TFL	Tables, Figures and Listings
Q-Q	Quantile-Quantile
CCI	[REDACTED]
ULN	Upper Limit of Normal
ULOQ	Upper Limit of Quantification
UN	Unstructured Covariance Structures
UNSCH	Unscheduled
WHO	World Health Organization
WHO-DD	World Health Organization- Drug Dictionary

AMENDMENT HISTORY

Date	Brief description of change
15SEP2020, v1.0	NA
28APR2021, v2.0	
Study design and sample size sections updated to be consistent with clinical study protocol (CSP) amendment 1.
 
Details for pre-interim analysis added.
 
Definition of analysis set updated following CSP amendment 1, especially CCI dose switching to CCI
 
Definition details and guidance reference added for computed tomography angiography (CTA) parameters.
 
List of fasting lipid parameters added.
 
Vital sign reference ranges added.
 
Tables and listings related to COVID pandemic added.
 
Sensitivity analysis without subjects having received both CCI added.
 
Some subgroup categories (geographical region, N terminal prohormone brain natriuretic peptide (NT-pro-BNP), CCI low density lipoprotein (LDL), left ventricular ejection fraction (LVEF)) added.
 
Specification of ADA analyses added.
 
Specific analyses for CCI added.
 
AE incidence by SOC and PT for bleeding and injection site reaction added.
 
ALT, AST and BILI elevations summaries added.

Date	Brief description of change
07MAR2022, v3.0	
Due to visit 9 removed in CSP amendment 2, visit 9 and following visits do not correspond to the same visit according to when patient was randomized. The visit “Day XX/Visit Y” were replaced by “Day XX” in all the SAP and Shells.
 
Variables removed from CSP amendment 2.0 are kept in the Statistical Analysis Plan (SAP) and will be analysed with descriptive statistics only (no statistical model, no figure, no subgroup analysis). Secondary endpoints removed from CSP amendment 2 are analysed as exploratory endpoints.
 
Since interim CTA at Day 122 was removed, only descriptive statistics will be provided at Day 122 for CTA parameters (no statistical model).
 
Everything that concerns interim analyses was removed especially section 5.
 
Analysis visit windows were added, and it was removed that nominal eCRF visits will be used in statistical analyses.
 
The rule for complete/partially missing start and stop dates of concomitant medication was updated.
 
For geometric mean calculation, an imputation rule was added for variables records with zero value.
 
It was added that the description of primary and secondary efficacy parameters will be studied over the course of the study using baseline value. In case of departure from the a priori distribution, the statistical analysis planned in this SAP will be updated.
 
Definitions of change from baseline (normal distribution), relative change from baseline (log-normal distribution) and percent change (any distribution) were added.
 
It was specified “one sided” before “p-value”, also “95% CI” was replaced by “90% CI”.
 
A listing on overdose was added.
 
Following sensitivity analyses were removed: LOCF and MMRM (not appropriate since interim CTA is removed). Sensitivity on patients without CTA assessment changed from baseline to Day 253 was added.
 
Some subgroup removed: CCI subgroup defined on tertiles were removed only medians were kept, repetition of subgroups on patients with reduced ejection fraction.
 
LLOQ value was updated to 0.0328 µg/mL.
 
CCI CCI [REDACTED]
 
Addition that the bioanalytical test site will have access to the randomization list.

1 STUDY DETAILS

1.1 Study objectives

The following endpoints in Table 1 will be evaluated in order to meet the objectives of the study.

Table 1 Objectives and Endpoints

Objectives	Endpoints
Primary	
To evaluate the effect of MEDI6570 on non-calcified coronary atherosclerotic plaques compared with placebo	Change from baseline to Day 253 in non-calcified plaque volume in the most diseased coronary segment (NCPV _{MD}), as measured by CTA imaging
Secondary	
To evaluate the effect of MEDI6570 on a surrogate biomarker of HF compared with placebo	Change from baseline to Day 253 in NT-proBNP
To evaluate the effect of MEDI6570 on left ventricular systolic function compared with placebo	Change from baseline to Day 253 in: 
• LVEF• GLS as measured by echocardiography
To evaluate the effect of MEDI6570 on left ventricular systolic function among participants with reduced ejection fraction (defined as <50%) compared with placebo	Change from baseline to Day 253 in: 
• LVEF• GLS as measured by echocardiography
To evaluate the effect of MEDI6570 on other measures of non-calcified coronary atherosclerotic plaque compared with placebo	Change from baseline to Day 253 in: 
• Global non-calcified plaque volume• Low attenuation plaque volume as measured by CTA imaging
To evaluate the immunogenicity of MEDI6570	
• ADA incidence• Titre as measured in serum during the intervention and follow-up periods
To evaluate the PK of MEDI6570	MEDI6570 concentrations as measured in serum during the intervention and follow-up periods

Objectives	Endpoints
Safety	
To assess the safety and tolerability of MEDI6570 compared with placebo	
During the treatment and follow-up periods:
 
 • AEs • Clinically important changes in: 
 Vital signs ECGs Safety laboratory assessments
Exploratory	
CCI	

ADA, anti-drug antibody(ies); AE, adverse event; CTA, computed tomography angiography; CDV, cardiovascular; ECG, electrocardiogram; CCI (ratio); GLS, global longitudinal strain; HF, heart failure; CCI (ratio); LVEF, left ventricular ejection fraction; CCI (ratio); MI, myocardial infarction; NCPV_{MD}, non-calcified plaque volume in the most diseased coronary segment, NT-proBNP, N-terminal prohormone brain natriuretic peptide; PK, pharmacokinetic(s); SAE, serious adverse event; CCI (ratio);

Some parameters are no longer listed as objectives and endpoints following CSP amendment 2 CCI (ratio); but summary statistics are still required for patients enrolled under CSP V1 and CSP amendment 1. Thus, they are not listed in Table 1 but can be found in Sections 3 and 4 as exploratory endpoints.

1.2 Study design

This is a Phase IIB, randomized, double-blinded, placebo-controlled, parallel-group, multicenter, international study to evaluate the efficacy, safety, pharmacokinetics (PK), and immunogenicity of MEDI6570 in subjects 30 to 365 days post MI with persistent inflammation defined as high sensitivity C-reactive protein (hs-CRP) ≥ 1 mg/L. Participants will be randomized to receive [REDACTED] (in an injection volume of 1.5 mL), or [REDACTED] (in an injection volume of 4.0 mL) MEDI6570 subcutaneously (SC), or an injection/volume-matched placebo (1.5 or 4.0 mL) every 4 weeks (Q4W) for 32 weeks (9 doses in total). Approximately 400 participants will be randomized [REDACTED]

[REDACTED] Participants who were randomized to a study intervention under Protocol Version 1.0 or Amendment 1 (when there was also a [REDACTED] dose group) and were allocated a dosing volume of 0.5 mL will continue on their randomized study intervention ([REDACTED] MEDI6570, or its injection/volume-matched placebo) to the end of the study, and the study blind will be maintained with regard to active versus placebo. The randomization will be stratified by geographic region (Asia, North America and Rest of the World) and by statin therapy status (no, low- or moderate-intensity statin therapy vs high-intensity statin therapy) at baseline.

The study will be conducted at approximately 70 to 100 study sites across Europe, Asia, Australia, and North America.

Subjects will be enrolled in the study for up to approximately 12 months, comprising an optional pre-screening period of up to 42 days (6 weeks), a screening and pre-randomization period of up to 42 days (6 weeks), a treatment period of 225 days (31 to 32 weeks), and a follow-up period of 100 days (approximately 14 weeks). Following screening and confirmation of eligibility, subjects will undergo an echocardiogram and (Coronary) computed tomography angiography (CTA) scan before randomization. The first dose of study treatment will be administered on Day 1 (Visit 3), after randomization. During the follow-up period, subjects will undergo an echocardiogram and CTA scan.

An Independent Data Monitoring Committee (IDMC) will review safety data from this study. A separate charter establishes the rules, meeting frequency, and scope of responsibilities of the IDMC. The report that will be received by the IDMC to evaluate safety will contain some of the TFL listed in this Statistical analysis plan (SAP).

[figure not shown]
No formal interim analysis is planned.

An analysis restricted to PK (serum MEDI6570 concentration) and PD [REDACTED] [REDACTED] data, will be performed after approximately 80 participants have completed the Day 57 (Visit 6), to evaluate the PK data and

the PK-PD relationship. Non-study personnel who have no other involvement in the study will perform this evaluation. These PK and PD data will be reviewed in conjunction with the safety data by the independent IDMC.

1.3 Number of subjects

The 3 injection/volume-matched placebo groups will be pooled for the analyses. CCI

2 ANALYSIS SETS

2.1 Definition of analysis sets

There are 9 populations defined for this study (Table 2).

Table 2 Populations for Analyses

Population	Description
All enrolled subjects	All enrolled subjects include those who have signed the informed consent form (pre-screen ICF or screen ICF).
Intent-to-treat (ITT) Population *	All randomized subjects will be included in the Intent-to-treat (ITT) Population. Subjects will be analysed according to their randomized treatment group. Subjects initially randomized to the CCI group who consented CSP amendment 1 and should switch dose to CCI will be analysed according to the CCI group.

Population	Description
As-treated population*	
Randomized subjects who received any study treatment will be included in the As-treated Population. Subjects will be analysed according to the actual treatment they received, regardless of their randomized treatment group. Subjects treated within the CCI group that received at least one CCI dose during the study will be analysed according to the CCI group.
 
If a patient received incorrect study drug for only a part of the treatment duration but also received correct study drug for the remaining time, the associated as-treated group for that patient will be the treatment group the patient was randomized to.

CTA Analysis population	
Subjects within the ITT population who have interpretable** CTA scans at baseline and at Day 253 or at Day 122 will be included. (Note that separate analyses will be conducted for Day 253 and Day 122).
 
Subjects will be analysed according to their randomized treatment group.

Per-protocol CTA analysis population	
Subjects in the CTA Analysis Population who received at least 3 doses of study treatment will be included in the Per-protocol CTA Analysis Population.
 
Subjects will be analysed according to the actual treatment they received.

Echocardiogram population Analysis	
Subjects within the ITT population who have interpretable echocardiograms in the baseline and follow-up periods will be included in the Echocardiogram Analysis Population.
 
Subjects will be analysed according to their randomized treatment group.

CCI	[REDACTED]
PK population	
All subjects who received ≥ 1 dose of MEDI6570 and have ≥ 1 one post-dose evaluable MEDI6570 serum concentration will be included in the PK population.
 
Subjects will be analysed according to the actual treatment they received. Subjects who received both CCI doses during the study will be analysed as a separate CCI group.

Immunogenicity population	
Subjects included in the As-treated Population who have ≥ 1 immunogenicity sample will be included in the Immunogenicity Population.
 
Subjects will be analysed according to the actual treatment they received.

* All subjects randomized in initial CSP accepted CSP amendment 1 and took at least one dose under CSP amendment 1. This means that any subject initially randomized in **CCI** have taken at least one dose of **CCI**

**An interpretable CTA scan is defined as having 1 or more matching evaluable segment at baseline and at Day 253 or at Day 122. LOCF (Last Observation Carried Forward) method not applied. The baseline scan must have quantifiable plaque present after segment matching to be interpretable. Programming specifics on matching evaluable segments are detailed in a separate CTA imaging guidance document (Version 4.0).

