6.3 Measures to Minimize Bias: Randomization and Blinding

6.3.1 Randomization Procedure

Participants will be randomized to an intervention group to minimize bias.

Randomization will be performed after the blood and urine samples are collected on Day 1 (Visit 3).

A 3-stage randomization procedure will be implemented:

- 1 Participants will first be grouped into strata according to geographic region (Asia, North America and Rest of World).
- 2 Then, within each geographic region, participants will be grouped into strata according to the status of their statin therapy intensity at baseline (no, low- or moderate-intensity statin therapy, vs high-intensity statin therapy; refer to [Appendix F](#)).
- 3 Then, within each stratum, participants will be assigned randomly to an intervention group according to randomization schedules using an RTSM system.

Before the study starts, the instructions for the RTSM will be provided to each site.

Re-allocation of participants to a dosing volume (Protocol Amendment 1): As a result of removing the [REDACTED] mg dose and introducing the [REDACTED] mg dose in Amendment 1, all participants enrolled under Protocol Version 1.0 were re-allocated to the appropriate dosing volume for their randomized intervention group under Amendment 1. Participants originally randomized to the [REDACTED] mg MEDI6570 group under Protocol Version 1.0 who had not completed treatment were switched to the [REDACTED] mg MEDI6570 group under Amendment 1. Participants originally randomized to the placebo group and who had not completed study treatment were re-randomized to one of the 3 injection/volume-matched placebo groups under Amendment 1.

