An independent DMC will be appointed. The DMC will be responsible for safeguarding the interests of the participants, by assessing the safety of the intervention during the study and for reviewing the overall conduct of the study. The DMC will have access to the individual treatment codes and allocated doses and will be able to merge these with the collected study data while the study is ongoing. The DMC will review prespecified data (including the effects of the increased dose from CCI [REDACTED] mg MEDI6570) periodically to ensure participant safety and make recommendations to the sponsor regarding further conduct of the study. This recommendation will be relayed to the sponsor's safety review committee and appropriate action will be taken. The DMC will have scheduled meetings at study initiation and at predefined study milestones with greater frequency during the initial part of the study. A separate charter will establish the rules, meeting frequency, and scope of responsibilities of the DMC.

A 6 Dissemination of Clinical Study Data

A description of this clinical study will be available on <http://astrazenecaclinicaltrials.com> and <http://www.clinicaltrials.gov> as will the summary of the study results when they are available. The clinical study and/or summary of study results may also be available on other websites according to the regulations of the countries in which the study is conducted.

A 7 Data Quality Assurance

- All participant data relating to the study will be recorded on an eCRF unless transmitted to the sponsor or designee electronically (eg, laboratory data). The investigator is responsible for verifying that data entries are accurate and correct by physically or electronically signing the eCRF.
- The investigator must maintain accurate documentation (source data) that supports the information entered in the eCRF.
- The investigator must permit study-related monitoring, audits, IRB/IEC review, and regulatory agency inspections and provide direct access to source data documents.
- Monitoring details describing strategy (eg, risk-based initiatives in operations and quality such as Risk Management and Mitigation Strategies and Analytical Risk-Based Monitoring), methods, responsibilities and requirements, including handling of non-compliance issues and monitoring techniques (central, remote, or on-site monitoring) are provided in the Monitoring Plan or contracts.

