4.2.8.1.2 Sensitivity analysis of the primary efficacy endpoint

All the tables and figure for analysis of primary efficacy endpoint presented in section 4.2.8.1.1 will be repeated with the aim to consolidate the results obtained with the previous ANCOVA model and with summary statistics.

The following sensitivity analyses will be performed on the per-protocol CTA analysis population:

- The same ANCOVA model (sensitivity analysis 1);
- The same ANCOVA model restricted to those who completed treatment (no missing treatment at Day 253) (sensitivity analysis 2);

The following sensitivity analyses will be performed on the CTA analysis population:

- The same ANCOVA model but without subjects having received both CCI [REDACTED] and CCI [REDACTED] (sensitivity analysis 3);
- The same ANCOVA model restricted to subjects with no scanner change between baseline and Day 253 (sensitivity analysis 4).

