4.2.10.7 Adverse events

After having assigned the AEs to the corresponding analysis phase as described in section [3.3.5.1](#), the AEs will be summarized for each treatment group and overall (total will not include placebo subjects). The AEs tables will be based on the as-treated population except the AE by ADA tables which will be based on the Immunogenicity population. Summary tables will include AEs in the on-treatment phase and AEs in the follow-up phase.

Summary tables are listed below.

An overview table containing:

- Number and percentage of subjects with any AEs
- Number and percentage of subjects with any AEs with outcome of death
- Number and percentage of subjects with any SAE (including events with outcome = death)
- Number and percentage of subjects with any AEs leading to discontinuation of treatment
- Number and percentage of subjects with any AEs leading to withdrawal from study

Subjects with multiple events in the same category are counted only once in that category.
Subjects with events in more than 1 category are counted once in each of those categories.

An overview table containing:

- Any AE
- Any AEs with outcome of death
- Any SAE (including events with outcome of death)
- Any AE leading to discontinuation of treatment
- Any AE leading to withdrawal from study

Multiple events in the same category are counted multiple times in that category. Multiple events belonging to more than 1 category are counted multiple times in each of those categories.

The following summary tables will be presented by SOC and PT:

- The number and percentage of subjects with any AEs
- The number of AEs
- The number and percentage of subjects with AEs with outcome of death
- The number of SAEs
- The number and percentage of subjects with SAEs
- The number and percentage of subjects with SAEs, assessed by investigator as possibly related to investigational product
- The number and percentage of subjects with AEs leading to discontinuation
- The number and percentage of subjects with any bleedings (all events from bleeding event form or from adverse event form with SMQ= “Haemorrhages narrow”)
- The number and percentage of subjects with any injection site reactions (all events from ISR form or from adverse event form with HLT= “Injection site reactions”)
- Overall summary of number and percentage of subjects with any AEs by ADA (anti-drug antibody category)
- The number and percentage of subjects by ADA (anti-drug antibody category)

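### For participants switched to the increased dose, adverse events that began before the switch are tabulated under the increased dose, and no planned safety summary separates or excludes these participants

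*SAP*

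**What the plan says.** **Grouping.** SAP 2.1, Table 2, As-treated population: "Subjects treated within the CCI group that received at least one CCI dose during the study will be analysed according to the CCI group". Protocol 9.3, Table 11, has the same rule. The Table 2 footnote adds: "All subjects randomized in initial CSP accepted CSP amendment 1 and took at least one dose under CSP amendment 1".

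**The switch.** Protocol 6.3.1 says that participants on the original high dose "who had not completed treatment were switched to the [REDACTED] mg MEDI6570 group under Amendment 1". Protocol Appendix A 5 shows that this was an increase, since the data monitoring committee (DMC) reviews data "including the effects of the increased dose from CCI" and so on.

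**Adverse events.** SAP 4.2.10.7: "The AEs tables will be based on the as-treated population except the AE by ADA tables"; those exceptions use the Immunogenicity population, where switchers are grouped in the same way (SAP 4.1). Under SAP 3.1.3 and 3.3.5.1 an AE is placed in the pre-treatment, on-treatment or follow-up phase by the first and last dose of study treatment. The summary tables take the on-treatment and follow-up phases.

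**Handling of the same participants elsewhere.** For PK, SAP 2.1 says: "Subjects who received both CCI doses during the study will be analysed as a separate CCI group". For the primary endpoint, SAP 4.2.8.1.2 plans "The same ANCOVA model but without subjects having received both" dose levels. SAP 4.2.8.2.1 and 4.2.8.3.1 plan the same exclusion for NT-proBNP and LVEF.

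**The concern.** A switcher has two stretches of treatment, one at the discontinued dose and one at the increased dose. The as-treated rule joins them and labels the whole with the increased dose. A single injection at that level, out of nine planned, is enough. An event with onset in the first stretch then appears under a dose that the participant had not yet received.

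The trial is described as dose-range finding, so the AE profile of its highest dose is one of its outputs. SAP 4.2.10.7 sends the same AE tables to the independent monitoring committee and to the final report. Mixing can add pre-switch events to the increased-dose column. It can also dilute that column with people who spent little time at that dose. The summary tables cannot show which has happened.

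Injection-site reactions are the clearest case. The amendment history in Protocol Appendix I records that the high-dose group moved from three injections totalling 2.5 mL to two totalling 4 mL. A reaction before the switch therefore arose under a different injection scheme as well as a different dose.

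**Working it through.** The plan states no figure to reproduce. The check follows the rules in order and then gives a sense of scale.

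**Following one event through the rules**

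1. A participant is randomized to the original high dose under Version 1.0, starts treatment, and is switched part-way (Protocol 6.3.1).
2. Such a participant took at least one increased dose (SAP Table 2 footnote), so the as-treated group is the increased dose. No one initially randomized to the discontinued dose remains in a group of its own.
3. An AE begins after the first study dose and before the first increased dose. It falls on or after the first dose of study treatment, so it is on-treatment (SAP 3.1.3, 3.3.5.1) and treatment-emergent (SAP 3.3.5.1).
4. The AE tables use the as-treated group (SAP 4.2.10.7; Protocol 9.4.3). The event is counted under the increased dose.
5. No rule in SAP 3.3.5.1 or 4.2.10.7 refers to the dose level at onset. The tables of key subject information measure time from the first dose of treatment, not from the switch.
6. The incorrect-study-drug sentence in the same Table 2 cell does not alter this, because the switch was planned under Amendment 1.

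**Scale (assumed counts)**

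Inputs: planned group size 123 (Protocol 4.1), taken here to include switchers; 9 planned doses (Protocol 4.1); *s* switchers, assumed. Each took at least one increased dose, so at most 8 of 9 doses were at the old level.

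- Share of the column = *s*/123
- Largest share of planned doses at the old level = 8*s*/(9 × 123) = 8*s*/1107

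| *s* (assumed) | Share of column | Largest share of doses at old level |
|---|---|---|
| 3 | 3/123 = 2.4% | 24/1107 = 2.2% |
| 5 | 5/123 = 4.1% | 40/1107 = 3.6% |
| 10 | 10/123 = 8.1% | 80/1107 = 7.2% |
| 20 | 20/123 = 16.3% | 160/1107 = 14.5% |

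One participant moves a row by 1/123 = 0.8 percentage points. The row for 20 is a stretch, given that SAP 4.1 describes the group as few.

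**The case against.** **The rule is prespecified, and the two documents agree.** This stands. A reader might infer a contradiction between protocol and SAP, but there is none. Classifying each person once, by the highest dose received, is a recognisable convention. It keeps one denominator per person, and it loads extra events onto the higher dose rather than losing them.

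**There are safeguards.** These also stand. SAP 4.1 has the number of switchers specified for the safety and efficacy analyses. Every AE (SAP 4.2.10.7) and every administration of study product (SAP 4.2.5.2) is listed, so onset can be related to the switch by hand. Under Protocol Appendix A 5 the DMC can merge individual treatment codes and allocated doses with the study data. A reader might infer that the DMC cannot assess the dose increase, and the documents do not support that. The DMC charter and the table shells are not available, so further detail there cannot be ruled out.

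**Safety is not singled out.** Partly right. The PK group of switchers appears in listings only (SAP 4.1). The efficacy exclusions do not cover global NCPV or LAPV (SAP 4.2.8.1.4) or GLS (SAP 4.2.8.3.1). Even so, three efficacy endpoints have an analysis without switchers and no safety table does.

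**The effect could be negligible.** Probably small, but its size is unknown. A reader might infer that misplaced events would change the apparent AE profile, for example by moving a preferred term from 4/123 = 3.3% to 7/123 = 5.7%, past the 5% threshold for the most-common table. That needs three switchers with the same term before the switch. This would be all of them if there are 3, or 30% if there are 10, against 4/113 = 3.5% in the other participants. The full tables by system organ class and preferred term show every term in any case.

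**Conclusion.** The point holds in a limited form. Treatment-emergent AEs that began before a switcher's first increased dose are tabulated under the increased dose, and no planned safety summary separates or excludes these participants. It does not extend to all AEs: events before the first study dose belong to the pre-treatment phase and are left out of the summary tables.

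The effect is probably small. On the assumed 3 to 10 switchers in 123, they are 2.4% to 8.1% of the column. The true count is not readable, and no event count can be taken from the documents. For a rare serious event, a single misplaced case could still matter to a reader of the table.

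Nor would any table in so few people reliably show whether AEs changed after the increase, because time before and after the switch is confounded with time on treatment. This is a low-cost improvement to reporting, not a flaw that invalidates the safety analysis.

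**What to change.** Keep the as-treated rule for the main tables. In SAP 4.2.10.7 add:

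- Supportive repeats of the AE overview, SAE, bleeding and injection-site reaction tables, excluding participants who received both dose levels from numerator and denominator alike. This mirrors SAP 4.2.8.1.2, 4.2.8.2.1 and 4.2.8.3.1.
- A listing of switchers' AEs that flags onset before, or on or after, the first increased-dose injection. Where a partial start date cannot be placed relative to that injection, flag it as undetermined rather than rely on the imputed date from SAP 3.1.1.2.

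Reassigning events by dose at onset within the main tables is tempting but worse. It would drop switchers' early events from the increased-dose numerator while the same people stay in the denominator. In the illustration above with 10 switchers, that gives 4/123 = 3.3%, whereas full exclusion gives 4/113 = 3.5%. The gap is small here, but it always lowers the rate for the highest dose.

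The cost is four supportive tables, one listing and a short SAP addition. AE start dates (Protocol 8.3.2) and dosing dates (Protocol 6.4) are already collected. In the repeats the increased-dose column would fall from 123 to between 120 and 113 on the assumed counts.
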